## 9.3 Multivariate analysis

If, despite randomisation, differences between important baseline-variables exist between groups allocated to placebo and to BoNT, multivariate regression analyses (logistic, linear, mixed effects, when appropriate) will be performed to adjust for imbalanced baseline variables.

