# Study population

A total of 54 patients with one or more jerks of psychogenic origin will be included in the study. To be included, patients need to experience to be significantly impaired in daily functioning due to at least one specific jerk. For the trial phase of the study, patients will be randomized in a 1:1 ratio to treatment with BoNT or to treatment with placebo. After 16 weeks, when the trial phase of the study is over, all patients will be included in the study on the long-term effect of treatment. Patients with serious complications during the trial period will not be included in second part of the study. For our fMRI sub-study approximately 16 patients of our total study population will be included. They will be compared to 16 neurologically and psychiatrically healthy volunteers.

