## 4.4 Sample size calculation

No prior results are available to clearly base the sample size calculation on. Hence, we chose to base our calculation on an expected difference in proportions reaching the primary endpoint between treatment with BoNT and placebo. For the expected proportions, we took the results of two prior trials studying the effect of BoNT into account. First, a trial in writer's cramp showed an effect in 32% of patients allocated to placebo and in 70% of patients allocated to BoNT on a patient rated primary endpoint. 11 Second, a cross-over trial in patients with motor tics showed no change in tics per minute in patients treated with placebo. Patients with tics and dystonia often have concurrent psychiatric disease as well. 12, 13 As the placebo effect may be large in patients with psychogenic disorders,  we expect that approximately one third of patients allocated to placebo treatment and approximately two thirds of patients allocated to BoNT may reach the primary endpoint. A two group Chi-square test with a 0,05 two-sided significance level will have 80% power to detect the difference between a control group proportion of 0,30 and a treatment group proportion of 0,70 (odds ratio of 5,4) when the sample size in each group is 24. As the side effects of therapy are mild and self-limiting and because only two injections are given in the trial period, we expect practically no withdrawals in this phase of the study. Assuming a withdrawal rate of 10 percent, we plan to include 27 patients per treatment arm, which means 54 patients in total.

This sample size calculation only concerns the trial part of this study, no power analysis was done for the follow-up study.

Regarding the fMRI study approximately 16 of the 54 patients participating in the BonT study will be included to take part in the fMRI study. Based on a study by Thirion et al., a minimum of 16 subjects is required for fMRI studies (see also amendment 2).

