Outcome measures 2, 5, 6, and 7 will be completed by the patients. Measure 1, 3 and 4 will be based on the video recordings and will be completed by the same independent investigator who is blind to treatment and is not involved in the injections based on the video of the patients. The psychiatric evaluations will be performed by a neuropsychologist specifically trained to perform the MINI-plus psychiatric interview.

A time schedule of the study is presented at page 14. For the trials secondary outcome measures, similar to the primary outcome measure, the difference in scores between baseline and after 16 weeks (4 weeks after the second injection) will be used. To evaluate the long term effect of treatment with BoNT the different outcome measures assessed 16 months after the start of the study (approximately 1 year after the end of the trial) will be compared with baseline (t=0) and with the assessments at the end of the trial period (t=16 weeks)

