## 9.2 Univariate analysis

An intention to treat analysis will be performed with regard to the trial results. The difference in the proportions of patients reaching the primary outcome measure between the groups treated with BoNT and with placebo will be assessed using the  $\chi 2$  statistic or Fisher's exact test, when appropriate. For the secondary outcome measures, proportional differences between the groups will be tested with the  $\chi 2$  statistic. Difference in continuous secondary outcome measures will be assessed with the Students t-test or ANCOVA. For the long term effects, the assessments of individual patients at t=16 months will be compared with previous assessments using tests for paired data (paired t-test, McNemar's symmetry  $\chi 2$  test for paired responses) or the mean difference between T = 16 months and T = 0. Finally, we will analyse repeated measures data using mixed effects models. In all analyses statistical uncertainties will be expressed in 95% confidence intervals.

Concerning the fMRI study the main study outcome measure is the difference in BOLD signal between scans of patients with psychogenic jerks before and after treatment with BoNT. Secondary outcome will be patterns of representations of external space and body scheme in patients compared to the patterns seen in healthy subjects. Another secondary outcome will be the performance of patients in the self-referenced and target-based finger movement task itself.

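### Covariate adjustment is triggered by observed baseline imbalance, and continuous secondary outcomes may be tested by t-test on change; fix the covariates in advance and use ANCOVA

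*Protocol*

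**What the plan says.** Protocol 9.3 (Multivariate analysis) reads "If, despite randomisation, differences between important baseline-variables exist between groups allocated to placebo and to BoNT, multivariate regression analyses" and continues that these models will adjust for the variables found to be imbalanced. It does not list the important variables, define a difference, or say whether the adjusted or unadjusted result prevails.

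Protocol 9.2 (Univariate analysis) fixes the primary comparison as a difference in proportions tested by chi-square or Fisher's exact test. For the other outcomes it says: "Difference in continuous secondary outcome measures will be assessed with the Students t-test or ANCOVA". It gives no rule for choosing between the two. Protocol 7.1.2 says that for the secondary outcomes "the difference in scores between baseline and after 16 weeks (4 weeks after the second injection) will be used".

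Protocol 7.2 stratifies randomisation by jerk location (extremity or abdominal). No analysis in Section 9 names that factor.

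**The concern.** Two choices are left until the baseline and outcome data are in view.

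The first is whether to adjust, and for what. In a randomised comparison an observed baseline difference is a chance event. Whether adjustment helps depends on how strongly a variable predicts outcome, and the size of the imbalance does not reveal that. Under the Section 9.3 rule, a strongly prognostic score that happens to be balanced is left out, and an irrelevant one that happens to differ is put in. The jerk-location stratum is balanced by design, so the trigger will tend to omit the one factor the design treats as important.

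The second is the test for continuous secondary outcomes. A t-test on change and an ANCOVA give different estimates and intervals from the same data, and the Protocol permits either. The t-test on change is the less precise of the two whenever the baseline to week-16 correlation is below 1.

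At stake are precision on the secondary outcomes and a single determined result for each of them. For the primary outcome, a second result of undefined standing may appear beside the planned test.

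**Working it through.** **The plan's own figure.** Section 4.4 states: "A two group Chi-square test with a 0,05 two-sided significance level will have 80% power", with response proportions of 0.30 and 0.70, "when the sample size in each group is 24".

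- n per arm = [1.96·√(2·0.5·0.5) + 0.8416·√(0.3·0.7 + 0.7·0.3)]² / 0.40² = (1.386 + 0.545)² / 0.16 = 23.3, so 24. Power at 24 per arm is 81.2%.
- Odds ratio = (0.7/0.3)/(0.3/0.7) = 5.44.
- With 10% withdrawal, 24/0.9 = 26.7, so 27 per arm and 54 in total.

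All of this reproduces. It concerns an unadjusted chi-square test, so the size of the trial does not depend on the point made here.

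**Precision for a continuous secondary outcome.** Let s be the SD, taken as equal at baseline and week 16, and r the correlation between the two. The Protocol gives no r, so 0.3 to 0.7 is an assumed range.

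- t-test on change: variance 2s²(1−r)
- ANCOVA on the week-16 value: variance s²(1−r²)
- Ratio ANCOVA/change: (1−r²)/[2(1−r)] = (1+r)/2

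The power columns use 24 per arm and an assumed effect of 0.8 SD.

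| r | Change variance (s²) | ANCOVA variance (s²) | Ratio | Power, change t-test | Power, ANCOVA |
|---|---|---|---|---|---|
| 0.3 | 1.40 | 0.91 | 0.65 | 65% | 83% |
| 0.5 | 1.00 | 0.75 | 0.75 | 79% | 89% |
| 0.7 | 0.60 | 0.51 | 0.85 | 95% | 97% |

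To match ANCOVA on 54 patients, a t-test on change would need about 54/0.65 = 83, 54/0.75 = 72 or 54/0.85 = 64 patients. On the 48 evaluable patients behind the power statement the figures are about 48/0.65 = 74, 48/0.75 = 64 and 48/0.85 = 56. The formulas ignore the one degree of freedom spent on the covariate, which is negligible here.

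**Type I error.** This was simulated with no treatment effect and 24 per arm, using 20,000 runs for a continuous outcome at r = 0.3, 0.5 and 0.7.

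| Strategy | Two-sided type I error |
|---|---|
| Change t-test only | 4.5–5.1% |
| ANCOVA only | 5.0–5.1% |
| Better of the two | 6.9–7.6% |
| ANCOVA if baseline p<0.05, else change t-test | 3.7–4.7% |
| ANCOVA if baseline p<0.20, else change t-test | 3.1–4.3% |

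The mechanical triggers are conservative because they switch to ANCOVA in exactly the samples where chance imbalance would push the change score towards a false positive.

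For a binary outcome (3,000 runs), the uncorrected chi-square test alone rejects in about 6%. The better of chi-square and a logistic model with one of five baseline variables rejects in about 7.4–8.3%.

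**The case against.** **The primary analysis is not open.** A reader might infer from Section 9.3 that the primary result is itself chosen from the data. The text does not support that. Section 9.2 fixes the unadjusted test, the sample size rests on it, and Section 9.3 does not say that regression replaces it. A supportive analysis is the natural reading. What stands is that the ranking of the two results is not stated.

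**Adjustment is not confined to imbalance.** Section 9.2 offers ANCOVA with no imbalance condition and also plans mixed models for repeated measures. This is correct, but nothing commits the analysis to ANCOVA.

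**False positives.** A reader might infer that the imbalance rule inflates type I error. Applied mechanically it does not: the simulated rates are at or below 4.7%. The 6.9–7.6% requires an analyst who keeps the better of two results, which the Protocol leaves possible but does not propose.

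**How often the trigger would fire.** Ten independent variables tested at p<0.05 would give 1−0.95¹⁰ = 40%. This does not describe the trial. Section 9.3 sets no threshold, Section 9.1 plans only descriptive statistics, and the motor-severity scores are unlikely to be independent. No frequency can be given.

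**This is detail for an analysis plan.** A covariate list could properly wait for one. The imbalance trigger could not, because it is a rule the Protocol itself sets, and an analysis plan with pre-named covariates would have to depart from it.

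**Secondary outcomes are not powered.** This is true, and it limits the weight of the point. It is no reason to permit the less precise method when the better one is already named in the same sentence.

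**Conclusion.** The point holds in a limited form. Section 9.3 uses a poor criterion for adjustment and leaves the standing of the adjusted result undefined. Sections 9.2 and 7.1.2 together permit a less precise analysis of the continuous secondary outcomes. If that analysis is used, the ANCOVA alternative would have had 65%, 75% or 85% of its variance at r = 0.3, 0.5 or 0.7. These correlations, the equal SDs and the 0.8 SD effect behind the power figures are assumptions. The direction of the result holds for any r below 1 under equal SDs.

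The precision loss does not reach the primary outcome, because the CGI-I is itself a rating of change and has no baseline value. The harm is lost precision and analyst discretion on secondary outcomes, plus an unranked second result for the primary. It does not threaten the validity of the main test.

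**What to change.** 1. In Section 9.2, drop the t-test alternative for continuous secondary outcomes. Analyse each outcome with a scheduled baseline by ANCOVA on the week-16 value, with its own baseline and the jerk-location stratum as covariates, regardless of balance. Transform jerk counts or use a count model if they are skewed.
2. For an outcome with no scheduled baseline, adjust for stratum only. The visit scheme in Section 7.3.4 lists the VAS at week 16 but not at baseline. It also does not name the SF-36 among the baseline questionnaires, so confirm whether that is collected then.
3. In Section 9.3, replace the imbalance trigger with one pre-named supporting logistic model for the primary outcome: treatment and jerk-location stratum, with baseline CGI-S if numbers allow.
4. State that the Section 9.2 test remains the primary result whatever the supporting model shows.

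The cost is an amendment of wording. The stratum is known from randomisation, examiner-rated CGI-S, UMRS, PMD score and jerk count are on the baseline list, and the sample size stays at 54. There is a small downside. The logistic model estimates a conditional odds ratio, which is not the planned difference in proportions. It may also be unstable if the abdominal stratum, whose size the Protocol does not give, turns out small. For both reasons it should stay supportive.

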## 9.4 Interim analysis

NA.

## **10 ETHICAL CONSIDERATIONS**

# 10.1 Regulation statement

The study will be conducted according to the principles of the Declaration of Helsinki (version of 2008) and in accordance with the Medical Research Involving Human Subjects Act (WMO) and other guidelines, regulations and Acts. Data management, monitoring and reporting of the study will be performed in accordance with the ICH GCP guidelines. Technicians and data managers of the AMC Clinic Research Unit (CRU) will perform central data management using Oracle Clinical. Internet-based remote data capture will be used for entering, managing and validating data from the investigative sites. Oracle Clinical was designed to meet industry regulations, including: FDA 21CFR Part 11 Rule (1997), ICH; Good Clinical Practice: Consolidated Guideline (1997), and FDA Guidance for Industry "Computerized Systems Used In Clinical Trials" (1999).

## 10.2 Recruitment and consent

Patients will be recruited in several manners. First, the 20 patients with psychogenic jerks enrolled in an ongoing study focussing on the pathophysiology of jerky movement disorders will be evaluated for eligibility. Furthermore, suitable patients from our outpatient clinic will be asked to participate. Finally, movement disorder specialists from other clinics will be asked to refer suitable patients.

We will only ask those patients who did not object to being contacted for participation in clinical research. Possible subjects will receive an information letter and reply form by mail beforehand. Subjects who are willing possibly participate, are invited for an interview with the investigator at the hospital. Informed consent form will be signed by the subject in presence of the investigator. All patients that will be included in the BoNT treatment study at the UMC Groningen will be asked to participate in the fMRI study. Healthy controls will be recruited using flyers.

# 10.3 Objection by minors or incapacitated subjects

NA

# 10.4 Benefits and risks assessment, group relatedness

The different questionnaires used in our studies are considered to be mildly psychologically stressful. The medical intervention with BoNT is expected to be safe as BoNT has long been

used for numerous indications, mainly other movement disorders, with little side effects and few serious adverse events (see SPC).

A speculative potential risk factor concerns the underlying psychiatric co-morbidity in patients with psychogenic movement disorders. It is thought that motor symptoms in psychogenic movement disorders are an expression of underlying psychiatric symptoms/disorders. When motor symptoms disappear due to treatment with BoNT, patients may be faced with their underlying psychiatric illness or may develop other somatic symptoms to express their psychiatric disease. No previous studies are available to estimate the chance of this potential risk.

Psychogenic movement disorders gained very little attention from any discipline for a long time, especially with regard to research. Currently, neurologists more and more realise that psychogenic movement disorders are an important part of the movement disorder spectrum as well and feel the need for evidence based therapeutic options. This study will be one of the first randomized controlled trials in this population and the first studying the effect of botulinum toxin in patients with jerky movement disorders. The results may provide an entirely new treatment option in these patients.

Functional magnetic resonance imaging is a non-invasive and safe procedure and is very commonly used in clinical practice and research. This amendment to the study fits in with current studies at the department of Neurology at the AMC (MEC# 07/290). We can benefit from the experience in set-up and analysis from this study. Being able to perform prior and post treatment fMRI in this study will gain very relevant insights in effectiveness of the BoNT treatment, aswell as in pathophysiology and diagnostic possibilities of psychogenic jerks. And therefore will contribute largely to the BoNT study and to knowledge of the psychogenic jerks in general.

## 10.5 Compensation for injury

The investigator has a liability insurance which is in accordance with article 7, subsection 6 of the WMO.

The investigator (also) has an insurance which is in accordance with the legal requirements in the Netherlands (Article 7 WMO and the Measure regarding Compulsory Insurance for Clinical Research in Humans of 23th June 2003). This insurance provides cover for damage to research subjects through injury or death caused by the study.

1. € 450.000,-- (i.e. four hundred and fifty thousand Euro) for death or injury for each subject who participates in the Research;

- 2. €3.500.000,-- (i.e. three million five hundred thousand Euro) for death or injury for all subjects who participate in the Research;
- 3. €5.000.000,-- (i.e. five million Euro) for the total damage incurred by the organisation for all damage disclosed by scientific research for the Sponsor as 'verrichter' in the meaning of said Act in each year of insurance coverage.

The insurance applies to the damage that becomes apparent during the study or within 4 years after the end of the study.

# 10.6 Incentives

NA

## 11 ADMINISTRATIVE ASPECTS AND PUBLICATION

# 11.1 Handling and storage of data and documents

Data will be handled confidentially and according to the Dutch Personal Data Protection Act. Personal data will be encoded by using a case record number. Paper data will be stored as Case Record Forms in a Trial Master File and coded by case record number. Digital data will be stored in a database and will also be coded by case record number. A separate file will contain the data to link the case record number to personal data. The key to the code will be safeguarded by the investigator who is responsible for the inclusion of patients. Data will be accessible to the investigator and collaborating investigators and to monitors, auditors, the accredited METC and other competent authorities. Data, video material and human material will be kept for a period of 15 years.

## 11.2 Amendments

A 'substantial amendment' is defined as an amendment to the terms of the METC application, or to the protocol or any other supporting documentation, that is likely to affect to a significant degree:

- the safety or physical or mental integrity of the subjects of the trial;
- the scientific value of the trial;
- the conduct or management of the trial; or
- the quality or safety of any intervention used in the trial.

All substantial amendments will be notified to the METC and to the competent authority. Non-substantial amendments will not be notified to the accredited METC and the competent authority, but will be recorded and filed by the sponsor.

Two substantial amendments have been added so far:

- Amendment 1 startle reflex dd. 29-9-2011
- Amendment 2 fMRI dd. 8-8-2013
- Amendment 3 follow-up patients 22-12-2017
- Amendment 4 change principle investigator 17-1-2017

# 11.3 Annual progress report

The investigator will submit a summary of the progress of the trial to the accredited METC once a year. Information will be provided on the date of inclusion of the first subject, numbers

of subjects included and numbers of subjects that have completed the trial, serious adverse events/ serious adverse reactions, other problems, and amendments.

# 11.4 End of study report

The sponsor will notify the accredited METC and the competent authority of the end of the study within a period of 90 days. The end of the study is defined as the last patient's last visit.

In case the study is ended prematurely, the sponsor will notify the accredited METC and the competent authority within 15 days, including the reasons for the premature termination.

Within one year after the end of the study, the investigator/sponsor will submit a final study report with the results of the study, including any publications/abstracts of the study, to the accredited METC and the Competent Authority.

# 11.5 Public disclosure and publication policy

This trial will be registered at the Dutch Trial Register (Nederlands Trial Register; NTR). Any trial results will be made publically in peer-reviewed medical journals. Authors of the manuscripts will include the principal and collaborating investigators who have contributed to the trial.

